### e. Immunogenicity assessment sets.

The immunogenicity assessment population is defined as all enrolled patients who receive at least one dose of study medication and have ADA results reported for at least one time point.

### 9.2. Statistical Methods and Properties

### 9.2.1. Statistical Methods for Dose Escalation/De-Escalation

# 9.2.1.1. Part A Monotherapy

For the monotherapy portion of the study, a mTPI design  will be adopted for dose escalation and de-escalation determination. The mTPI design uses a Bayesian statistics framework and a beta-binomial hierarchical model with prior distribution of DLT set as a beta (0.75, 0.65) to compute the posterior probability of three dosing intervals that reflect the relative difference between the toxicity rate of each dose level to the target rate (pT=0.25, where pT is the target probability). If the toxicity rate of the currently used dose level is far smaller than pT, the mTPI will recommend escalating the dose level; if it is close to target probability (pT), the mTPI will recommend continuing at the current dose; if it is far greater than pT, the mTPI will recommend de-escalating the dose level.

Decision rules are based on calculating unit probability mass (UPM) of three dosing intervals corresponding to under, proper, and over dosing in terms of toxicity. Specifically, the under dosing interval is defined as  $(0; pT-e_1)$ , the over-dosing interval  $(pT+e_2;1)$ , and the proper-dosing interval  $(pT-e_1, pT+e_2)$ , where  $e_1$  and  $e_2$  are small fractions. Based on the safety profile of PF-04518600 as a single-agent in Study B0601002, both  $e_1$  and  $e_2$  are selected as 0.05. Therefore, the target interval for the DLT rate is (0.20, 0.30).

The three dosing intervals and the penalty functions are associated with three different dose-escalation decisions. The under-dosing interval corresponds to a dose escalation (E), over-dosing corresponds to dose de-escalation (D), and proper-dosing corresponds to remaining at the current dose (R). Given a dosing interval and a probability distribution, the unit probability mass (UPM) of that dosing interval is defined as the probability of a patient belonging to that dosing interval divided by the length of the dosing interval. The mTPI design calculates the UPMs for the three dosing intervals, and the one with the largest UPM informs the corresponding dose-finding decision, which is the dose level to be used for future patients. For example, if the under-dosing interval has the largest UPM, the decision will be to escalate, and the next cohort of patients will be treated at the next higher dose level. Ji et al.  have demonstrated that the decision based on UPM is optimal in that it minimizes a posterior expected loss (ie, minimizes the chance of making a wrong dosing decision).

The dose-finding portion of the study is terminated when either approximately 40 DLT evaluable patients have been enrolled or when at least 9 evaluable patients have been treated at the highest dose with mean DLT rate  $\leq 30\%$ , whichever comes first. Refer to Table 3 (Decision Rules) in Section 3.1.5.1 (Criteria for Dose Escalation Part A Monotherapy).

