Peripheral pharmacodynamic assessments of any given dose may be completed after the dose is deemed safe, and escalation to the next dose level has already occurred. When peripheral monitoring indicates immune modulation in the first 2-4 patients, the dose level will be expanded to approximately 10 patients allowing better characterization of pharmacodynamic effects and reducing variability due to small sample size. If no peripheral pharmacodynamic effects are observed for the first 2-4 patients in any dose level, the dose level will not be expanded.

Patients who are part of the expansion of any dose level will undergo mandatory pre- and on-treatment biopsies (See Schedule of Activities for specifics). To better estimate the OBD, tumor pharmacodynamic data from all patients will be evaluated at the end of Part A1.

Safety information provided by additional patients enrolled into each dose expansion cohort will be taken into account for RP2D determination. If the DLT rate is estimated to reach 30% or more at any dose level, enrollment at that level and all higher levels will be temporarily stopped and the safety data will be analyzed. Decision on moving forward will follow the same DLT target as described previously. Dose escalation will continue until an MTD has been established, maximum dose level (20 mg/kg, please see Section 3.1.5 Criteria for Dose Escalation) has been reached or until three sequential dose levels show a similar pharmacodynamic signal.

Late immune related DLTs that occur during the first 98 days (or first 7 cycles if patient remains on treatment) will be taken into account for MTD determination (see Section 3.2.1 Late Immune Related DLTs and Section 6.3 Follow-up Visit). If late immune related DLTs occur, all safety data will be reviewed and a decision will be made whether or not to permanently stop enrollment in the higher cohorts and declare the MTD, to continue enrollment in the cohort, to increase the number of patients evaluated in that cohort or to stop the study.

Dose levels selected for Part A2 are based on data from Part A1.

The proposed doses, schedule(s) and PK time points may be reconsidered and amended during the study based on the emerging safety and pharmacokinetic data. Lower, intermediate and higher dose cohorts (maximum of 20 mg/kg, refer to Section 3.1.5 Criteria for Dose Escalation) can be added. Higher dose cohorts can only be initiated if the next lowest level is deemed safe.

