An initial 2 to 4 patient may be enrolled initially into each dose level combination. Fresh biopsies will not be required for these patients. The mTPI model performs dose escalation by increasing or decreasing the dose of either PF-04518600, utomilumab or both based on the observed number and/or nature of DLTs at the current dose combination level (see Figure 5). The starting dose combination level will be 0.1 mg/kg PF-04518600 combined with 20 mg of utomilumab. If no DLTs are observed, the next dose combination level will be 0.3 mg/kg PF-04518600 combined with 20 mg of utomilumab. If no toxicity is observed, the dose of PF-04518600 will continue to be increased (see Figure 5). If toxicity is observed at the starting dose combination level, 0.1 mg/kg PF-04518600 combined with 10 mg of utomilumab will be evaluated. Subsequent to the initial dose, if dose de-escalation is recommended after evaluation, intermediate dose levels between the previous dose combination and current dose combination may be studied. Using the observed data, 1 or more dose combination levels of PF-04518600 and utomilumab with toxicity rate closest to,

\* If first 6 patients at the 0.3 mg/kg dose level in Part A1 OX40 monotherapy experience ≥ Grade 2 immune related toxicities or cytokine release syndrome, starting dose of PF-04518600 will be 0.01 mg/kg combined with 20 mg of utomilumab in Part B1.

\*\* Based on emerging data in the 10 mg/kg Part A1 cohort, an optional cohort of 10 mg/kg PF-04518600 in combination with 100 mg of utomilumab may be evaluated.

but not exceeding, the predefined target rate of 25% will be identified. If the starting dose is deemed not tolerable, the next dose combination level will be 0.1 mg/kg PF-04518600 combined with 10 mg of utomilumab.

When a dose combination level is deemed safe following a DLT observation period of 28 days or 2 cycles (of PF-04518600), escalation will occur to the next dose combination level. A staggered start will be employed for all dose combination levels; that is, the first patient for any dose combination level will be dosed, and observed for 48 hours before subsequent patients can be dosed. If no safety concerns arise during this 48 hr period, a second patient will be enrolled into the same dose combination level.

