#### 3.1.5. Criteria for Dose Escalation

## 3.1.5.1. Part A Monotherapy

A mTPI method, targeting a DLT rate of 25% and an acceptable DLT interval (20%-30%),  will be utilized in Part A1 dose escalation phase. Initial 2 to 4 patients will be enrolled in each cohort with a target size of 3 patients. In dose cohorts with 2 patients enrolled, an additional patient may be enrolled for dose escalation assessment if one of the two patients has a DLT event observed. Decisions to escalate to the next dose level will be determined using safety assessments obtained from these initial 2-4 patients.

The dose levels to be evaluated are listed in Table 2. Beginning with the starting dose of 0.01 mg/kg, if either a DLT related to PF-04518600 or a grade ≥2 cytokine release syndrome, infusion reaction, or allergic reaction is observed, subsequent dosages will not be increased by more than 3-fold, or one- half a log (eg, increases from 0.01 mg/kg will be to 0.03 mg/kg, and increases from 0.3 mg/kg will be to 1.0 mg/kg). If dosages greater than 3 mg/kg are evaluated, if DLTs are absent, subsequent dose levels may include a maximum of 5-fold increase. If a DLT considered related to PF-04518600 is observed, the next dose level will not be greater than 3-fold the previous dose level. Up to a maximum of 20 mg/kg may be evaluated. If a high DLT rate is observed at the starting dose, the study may be stopped.

Table 2.	Table	of Poter	itial Dose	Levels
Lame 4.	1 41115	WI I WIEL	IIIAI I I USC	I /C V C I S

Cohort	Dose (mg/kg)	
1	0.01	
2	0.1	
3	0.3	
4	1.5	
5	3	
6	TBD: maximum 6.0 (optional)	
7	10	

The mTPI method relies upon a statistical probability algorithm, calculated using all patients treated in prior and current cohorts at the same dose level to determine where future cohorts should be on dose escalation, no change in dose, or dose de-escalation.

The algorithm will stop if any of the following criteria is met:

1. The maximum sample size has been achieved (approximately 58 patients total).

- 2. A minimum of 9 patients have been accumulated on a dose that is predicted to be the MTD or MAD; or,
- 3. All doses explored appear to be overly toxic and the MTD cannot be determined.

All clinically relevant AEs and SAEs will be reviewed by the sponsor and investigators to determine if the dose allocation schedule requires modification.

**Table 3.** Decision Rules

	Number of Patients Treated at a Dose level										

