Number of Patients Having DLT	n=2	n=3	n=4	n=5	n=6	n=7	n=8	n=9	n=10	n=11	n=12
0	Е	Е	Е	Е	Е	Е	Е	Е	Е	Е	Е
1	n/a	S	S	S	Е	Е	Е	Е	Е	Е	Е
2	U	D	D	S	S	S	S	S	S	S	S
3		U	U	D	D	S	S	S	S	S	S
4			U	U	U	D	D	D	D	D	S
5				U	U	U	U	U	D	D	D
6					U	U	U	U	U	U	D
7						U	U	U	U	U	U

D: De-escalate the dose; E: Escalate the dose; S: Stay at the dose;

U: Unacceptable toxicity; n/a: Not applicable

Patients experiencing a DLT may be managed with dose modification (after dose interruption) or discontinuation. Subsequent dose levels may not be opened until the first 2-4 patients entered at the current dose level have been treated and observed for at least two complete cycles and the number of DLTs among those patients in their first two cycles has been determined.

If a patient withdraws from the study before Day 28 for reasons other than investigational product-related toxicity (see Section 3.2 DLT Definition), another patient may be enrolled to replace that patient at the current dose level. In principle, all patients must be evaluated for 28 days. However, if a patient withdraws close to Day 28 for reasons other than toxicity and is due to a clear unrelated drug event (eg, traffic accident, clear disease progression), the patient may be deemed evaluable for safety if safety assessments have been unremarkable.

and the investigator and sponsor's medical monitor both agree that the patient is evaluable for DLT safety observation.

The dose escalation portion of the study is completed when at least 9 evaluable patients have been treated at the highest dose associated with a mean DLT rate of 25%.

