#### 3.3. Maximum Tolerated Dose (MTD) Definition

The estimated MTD is the dose level associated with approximately 25% of patients experiencing DLT. The target interval for the DLT rate is 20%-30%. Due to the discreteness of the dose levels and in the interest of safety of patients, the estimated MTD is the highest tested dose level with mean DLT rate ≤0.25 in at least 9 DLT evaluable patients. This is with the exception of Grade 4 and 3 cytokine release syndrome, infusion reaction or allergic reaction. If  $\geq 1$  patient out of 6 (or  $\geq 17\%$ ) experiences a Grade 4 cytokine release syndrome. infusion reaction or allergic reaction, or if 2 patients out of 6 (33%) experiences Grade 3 cytokine release syndrome, infusion reaction or allergic reaction, the dose level will be considered to be above the MTD. All safety data will be evaluated and a decision will be made whether or not to permanently stop enrollment in the higher cohorts and declare the MTD, to continue enrollment in the cohort, to increase the number of patients evaluated in that cohort or to stop the study (see Section 3.2.1 Late Immune Related DLTs). The cumulative incidence of all late immune related DLTs will be taken into account for determination of the MTD/RP2D. An interim safety analysis will be triggered if the overall cumulative incidence of late immune related DLTs increases above 25% across all dose levels. If a clear dose response is observed, the study may resume enrollment at the lowest dose level with incidence in 1 or less patients out of 6. If the incidences of late immune related DLTs do not appear to have a dose response relationship (ie, consistently observed in all dose levels), the option to terminate the study will be considered.

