4. HYPOTHESES AND DECISION RULES

4.1. Statistical Hypotheses

This clinical trial implements a Bayesian procedure to determine the MTD. No classical hypothesis testing will be done. Decisions will be based on Bayesian posterior probabilities arising from a full hierarchical probability model.

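### Protocol 9.2.1.1 lets dose-finding end at a mean DLT rate of up to 30%, while the completion and MTD rules use 25%, so the search can stop at a dose that fails the MTD rule

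*Protocol*

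**What the plan says.** Protocol Section 9.2.1.1 gives two alternative triggers for ending Part A dose-finding. The second applies "when at least 9 evaluable patients have been treated at the highest dose with mean DLT rate" at or below 30%. The same sentence sends the reader to Table 3 in Section 3.1.5.1.

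Section 3.1.5.1 has its own completion rule. The escalation portion is "completed when at least 9 evaluable patients have been treated at the highest dose associated with a mean DLT rate of 25" percent. Its list of algorithm stop criteria asks for 9 patients on a dose predicted to be the MTD or the maximum administered dose, and contains no 30% criterion.

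Section 3.3 first states the 20% to 30% target interval. It then says that, because dose levels are discrete and for patient safety, "the estimated MTD is the highest tested dose level with mean DLT rate ≤0.25 in at least 9 DLT evaluable patients". Section 9.2.2.1 repeats this rule for Part A and Section 9.2.2.2 gives the same threshold for Part B. Part B takes its escalation scheme from 9.2.1.1 by way of 9.2.1.2, and 3.1.5.2 completes Part B at a DLT rate of 25%.

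Neither document defines the mean DLT rate. For Part B1, Protocol Section 3.1.2.1 points to raw data: "Using the observed data, 1 or more dose combination levels of PF-04518600 and utomilumab with toxicity rate closest to" but not above 25% are to be identified. SAP Section 4.1 points to the model: "Decisions will be based on Bayesian posterior probabilities arising from a full hierarchical probability model". The SAP states that it supersedes the protocol's statistical considerations. On this point, though, it repeats only the 25% target, the 20% to 30% interval and the decision table, and Section 7.2.1 refers MTD estimation back to the study design section.

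**The concern.** Establishing the MTD is the primary objective of Part A1. Two sections give different thresholds for finishing the search for it, and the looser one does not match the definition of what is being sought. A team applying 9.2.1.1 as written could close dose-finding at a dose whose rate lies above 25% and up to 30%. It would then find that Section 3.3 does not allow that dose to be named the MTD, while Table 3 still says to keep treating at it. Because the rate itself is undefined, the team could not even be sure which outcomes are affected.

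**Working it through.** **Inputs.** Stop threshold 30% with at least 9 evaluable patients (9.2.1.1). MTD threshold 0.25 with at least 9 evaluable patients (3.3, 9.2.2.1, 9.2.2.2). Prior Beta(0.75, 0.65), target 0.25 and proper-dosing interval 0.20 to 0.30 (9.2.1.1). Table 3 runs to n = 12, so the check covers n = 9 to 12.

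**Plan's own figures first.** Table 3 prints Stay for 2/9, 3/10, 3/11 and 3/12. Recomputing the unit probability mass from a Beta(0.75 + x, 0.65 + n − x) posterior over (0, 0.20), (0.20, 0.30) and (0.30, 1) also gives Stay for all four.

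**Conflict condition.** An outcome meets the stop rule and fails the MTD rule when 0.25 < rate ≤ 0.30. There are two candidate rates for x DLTs in n patients:

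- observed proportion: x/n
- posterior mean: (0.75 + x)/(1.4 + n)

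| x/n | Observed | Posterior mean | Conflict |
|---|---|---|---|
| 2/9 | 0.222 | 2.75/10.4 = 0.264 | posterior mean only |
| 3/9 | 0.333 | 3.75/10.4 = 0.361 | none |
| 2/10 | 0.200 | 2.75/11.4 = 0.241 | none |
| 3/10 | 0.300 | 3.75/11.4 = 0.329 | observed only |
| 2/11 | 0.182 | 2.75/12.4 = 0.222 | none |
| 3/11 | 0.273 | 3.75/12.4 = 0.302 | observed only |
| 3/12 | 0.250 | 3.75/13.4 = 0.280 | posterior mean only |
| 4/12 | 0.333 | 4.75/13.4 = 0.354 | none |

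No other count with n = 9 to 12 falls in the gap on either reading. The mismatch therefore exists whichever rate is meant, but in different cells.

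**Reachability.** Section 3.1.5.1 says "Initial 2 to 4 patients will be enrolled in each cohort with a target size of 3 patients". In cohorts of 3 the totals from the minimum of 9 are 9 and 12, and on observed proportions neither gives a conflict (2/9 and 3/12 pass both rules; 3/9 and 4/12 fail both). The observed-rate conflict needs 10 or 11 patients at a dose. Such totals do occur, because levels may be expanded to about 10 patients, and Section 3.1.1.2 reports 10 at 0.1 mg/kg and 11 at 0.3 mg/kg.

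**Interaction with the hold.** Section 3.1.1.1 adds: "If the DLT rate is estimated to reach 30% or more at any dose level, enrollment at that level and all higher levels" is temporarily stopped. An observed 3/10 = 30.0% meets that hold and the 9.2.1.1 stop at the same time.

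**Literal reading of 3.1.5.1.** A rate of exactly 25% needs n divisible by 4, so for n = 9 to 12 only an observed 3/12 satisfies it. The sentence needs an inequality.

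**After the fix.** With ≤25% in both places and one definition of the rate, no outcome can meet the stop rule and fail the rate part of the MTD rule. The definition is needed in its own right: 2/9 and 3/12 qualify as the MTD on observed proportions (22.2%, 25.0%) but not on posterior means (26.4%, 28.0%).

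**The case against.** The best defence is that ending the search and declaring the MTD are separate steps. On that view 30% is simply the top of the target interval: the design stops inside the interval and then selects, more strictly, the highest dose at or below 0.25. Protocol Section 9.6.1 and SAP Section 7.2.1 both send MTD estimation to the study design section, so 3.3 governs the declaration. This does not rescue the text, because 3.1.5.1 states the completion rule itself, not only the selection rule, at 25%. There are two completion rules for one escalation.

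Parts of the defence stand. The declaration rule is not in doubt. A lower dose can be declared if it has at least 9 evaluable patients, which is realistic given expansion to about 10 per level. On observed proportions, 3/10 is caught by the 30% hold and cohorts of 3 give no conflict.

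A reader might infer that the conflict arises easily in cohorts of 3 on the posterior-mean reading, through 1/3, 2/6 and 2/9, all printed Stay. The documents do not support treating that route as unobstructed. 1/3 and 2/6 are each 33% observed, with posterior means of 1.75/4.4 = 39.8% and 2.75/7.4 = 37.2%, so both meet the hold in 3.1.1.1. Support for the posterior-mean reading is also thin, since SAP 4.1 speaks of posterior probabilities for decisions and not of a posterior-mean DLT rate. No probability for the conflict is therefore offered.

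**Conclusion.** The point holds as a minor consistency error in a decision rule. The 9.2.1.1 threshold disagrees with 3.1.5.1, 3.3, 9.2.2.1 and 9.2.2.2, and nothing in the protocol or SAP reconciles them. For n = 9 to 12 it affects two outcomes on each reading of the rate: 3/10 and 3/11, or 2/9 and 3/12. The second pair rests on taking the stated prior and its posterior mean as the intended estimate.

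A reader might infer that an overly toxic dose could be declared the MTD, or that Part A1 could be left with no MTD. Neither follows: 3.3 blocks the first, and a lower dose with at least 9 evaluable patients can avoid the second. Nor is there sign of an effect on the data so far. Section 1.2.1.3 reports no DLTs in 52 Part A1 patients at the May 2017 cut-off, and with no DLTs both thresholds are met on either reading (at 0/9 the posterior mean is 0.75/10.4 = 0.072).

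**What to change.** - In 9.2.1.1, replace ≤30% with ≤25%. Section 9.2.1.2 carries the change to Part B.
- In 3.1.5.1 and 3.1.5.2, change the completion rate from 25% to ≤25%.
- In 3.3, 9.2.1.1, 9.2.2.1 and 9.2.2.2, state that the mean DLT rate is the observed proportion of DLT-evaluable patients with a DLT.

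Table 3 stays as printed. The cost is a threshold edit in three sections and one defining phrase in four. In conduct, a dose at 3/11 or 3/10 would need one or two further evaluable patients without a DLT to reach 3/12 = 25.0%, which is consistent with the Stay decision already printed and, at 3/10, subject to the existing hold.

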# 9.2.1.2. Part B Combination Therapy

The dose escalation scheme based on mTPI method described in Section 9.2.1.1 will also be used in Part B Combination Therapy.

# 9.2.2. Statistical Method for Estimating the MTD

### 9.2.2.1. Part A Monotherapy

As previously described, the estimated MTD is the highest tested dose level with mean DLT rate ≤0.25 in at least 9 DLT evaluable patients. It is also assumed that at the estimated MTD, less than 17% patients will experience Grade 4 cytokine release syndrome, infusion reaction or allergic reaction during the 28 day DLT observation period, and the first 98 days after initial treatment. It is also assumed that at the estimated MTD less than 33% of patients will experience grade 3 cytokine release syndrome, infusion reaction, or allergic reaction during the first 98 days after treatment. We assume that higher doses of either PF-04518600 result in higher toxicity rates. But, due to the relatively low number of patients that may be potentially allocated to any dose combination, this assumption may be violated.

# 9.2.2.2. Part B Combination Therapy

The estimated MTD is the highest tested dose combination level with mean DLT rate ≤0.25 in at least 9 DLT evaluable patients. It is also assumed that at the estimated MTD the toxicity of PF-04518600/utomilumab combination follows the monotonicity assumption that a higher dose level of either PF-04518600 or utomilumab will result in a higher toxicity rates.

# 9.3. Sample Size Determination

A maximum of approximately 210 patients are expected to be enrolled into the study. The total sample size is not based on formal hypothesis testing considerations.

